^h Return 24-hr urine

- Baseline visit and Final 2 visits: Ni, NAE, Cr
- Five 5-ml aliquots will be archived at the Baseline and Final 2 visits.

ⁱ Capsules of KHCO_3 /placebo and Ca/D supplements dispensed. Participants will take 1 capsule after each meal for 14 days (to adapt to the KHCO_3) and then increase to 2 after each meal (6/d total) thereafter.

^j Protein packets will be dispensed by the dietary team. Subjects will take the whey protein supplement with each meal except on the days 164 and 168 (Final Days 1 and 2) when they will skip the packet with their evening meal. The goal of the packets is to bring total intake of protein to 1.5 g/kg/d (or 15-25 g of additional protein with each meal depending on body weight).

^k Adherence to study pills will be assessed by capsule counts and by capsule diaries. Adherence to the protein packets will be assessed by packet counts and diaries. Objective measures of adherence are NAE and UNi.

Medical history questionnaire

The medical history includes medication and supplement use, general medical history, and past and current cigarette smoking and alcohol use. The questionnaire will be conducted in person or by telephone if preferred by the study participant.

Study interventions

Whey protein powder. Protein packets will contain 15-25g of whey protein each. We will advance all participants to

Weight category	A (< 70 kg)	B (70 – 90 kg)	C (91+ kg)
Dosing group	15g per meal	20g per meal	25g per meal

approximately 1.5 g/kg/d based on their body weight and typical baseline protein intake. The whey protein and its isocaloric placebo (maltodextrin - an easily digestible flavorless starch) powder will be flavorless and purchased in bulk at <http://www.bulkfoods.com>. The dietary team will make the packets and distribute to participants at baseline and weeks 6, 12, and 18. The packets will be mixed with water and the dietary team also will provide a menu for how to incorporate the powder into recipes. The whey and placebo powder packets will be isocaloric.

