KHCO_3 supplement. The 81 mmol of KHCO_3 is available in six 13.5 mmol capsules daily; an equal volume of microcrystalline cellulose (placebo) will be placed in 6 identical gelatin capsules. All capsules will be taken with 8-oz of water or the supplement drink immediately after meals. On days 1-14, participants will take 1 capsule after each meal (adaptation period to minimize risk of GI intolerance); thereafter, they will take 2 capsules after each meal (6/d). KHCO_3 capsules and matching placebo capsules will be purchased from Life Enhancement Products, Inc. (Reno, NV). Independent analysis by Eurofins (Madison, WI) will be carried out to verify contents.

Dietary intake assessment

Dietary telephone prescreening questionnaire – Usual protein intake in grams per day will be assessed with a two-item questionnaire developed in the NEPS laboratory to target individuals on no more than 0.8 g/kg/day of dietary protein. Each of the two questions has multiple parts. For example, participant responses to the following question: “How many servings of per day do you have of a) meat, poultry, and fish? b) eggs? c) dairy such as milk, yogurt and cheese?” For part a), think of a serving as being about the size of a deck of cards. For part c), think of a serving as a cup of milk or yogurt or 2 slices of cheese. The second question asks about vegetable and other non-animal protein foods. From servings, the questionnaire calculates g/d of dietary protein which we can then arrive at the g/kg/d with a body weight. This daily intake will be reviewed and confirmed at screening with an in-person dietary assessment.

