The investigator's central hypothesis is that higher protein intake and a neutralizing alkaline salt will improve muscle performance and mass, compared to their respective placebos, in older men and postmenopausal women. To test the hypothesis, the investigators conducted a randomized, double-blind, placebo-controlled, 2x2 factorial study in underactive men and women age 65 and older on baseline lower protein diets. Participants were assigned to one of four groups: either a whey protein (WP) supplement (to raise protein intake to 1.5 g/kg/d) with or without potassium bicarbonate (KHCO_3) 81 mmol/d or an isocaloric placebo supplement with or without KHCO_3 81 mmol/d for 24 wks.

b. *Objectives*

Primary aim: Evaluate the effects of whey protein (WP) and of KHCO_3 on lower extremity muscle power at 24 weeks. This factorial ("at-the-margins") analysis will evaluate the effects of WP vs. placebo-WP and of KHCO_3 vs. placebo- KHCO_3 by using an ANCOVA approach comparing the primary outcome between groups with adjustment for baseline lower extremity muscle power, sex, age and factorial design.

Secondary aims: Evaluate the effects of WP and of KHCO_3 in terms of lower extremity muscle power at 12 weeks, knee extension torque at 12 and 24 weeks, physical performance at 24 weeks, lean mass at 24 weeks, handgrip strength at 24 weeks, physical performance battery at 24 weeks, and 24-hr urinary nitrogen excretion (UNi).

4. Study Methods

a. *Trial design*

This is a single-center, individually randomized, 2x2 factorial, placebo-controlled trial.

Participants were randomized in a 1:1:1:1 fashion to:

- whey protein isolate + KHCO_3
- whey protein isolate + microcrystalline cellulose
- maltodextrin powder + KHCO_3
- maltodextrin powder + microcrystalline cellulose

b. *Randomization*

Randomization was stratified by sex, by using block randomization (randomly permuted block sizes of 4 or 8). The random allocation sequence was computer-generated by a biostatistician. The randomization sequence was incorporated into the online Electronic Data Capture system. Central randomization via the online EDC system maintained allocation concealment.

c. Sample size

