For all objectives, we use a superiority framework and a factorial analysis (at-the-margins analysis), i.e., testing the superiority of whey protein against no whey protein and of KHCO₃ against no KHCO₃.

e. Statistical interim analyses and stopping guidance

No formal statistical interim analysis was planned. The Data and Safety Monitoring Board (DSMB) periodically evaluated enrollment data, AE, and SAE by randomization group.

f. Timing of final analysis

Final analysis will take place after all data for the primary and secondary outcomes have been collected, data cleaning is complete, and after this SAP is finalized and posted on clinicaltrials.gov.

g. Timing of outcome assessments

Outcomes are measured at baseline, 12 weeks, and 24 weeks after randomization.

5. Statistical Principles

a. Confidence intervals and P values

All statistical tests will be 2-sided. We will use $p \leq 0.05$ to indicate statistical significance for the primary outcome for each of the two primary comparisons of interest in a factorial analysis (at-the-margins analysis): a) the comparison between all participants allocated to KHCO₃ vs. all those not allocated to KHCO₃ and b) the comparison between all participants allocated to whey protein vs. all those not allocated to whey protein. Under the assumption of no interaction that is inherent to a factorial analysis, the primary analyses test two independent hypotheses, and no multiplicity adjustment is needed in this scenario. All secondary and exploratory analyses are considered as supporting the primary analyses, with two-sided tests and significance levels of 0.05.

b. Adherence and protocol deviations

Adherence to study pills was assessed by capsule counts and by capsule diaries. Adherence to the protein packets was assessed by packet counts and diaries. Objective measures of adherence are urinary net acid excretion (NAE) and UNi.

Major protocol deviations for the trial include:

1. Participant found ineligible after randomization
2. No informed consent signed
3. Participant didn't receive the randomly allocated intervention
4. Withdrawal of consent for future data collection, and/or ongoing use of previously collected study data

c. Analysis populations

The full analysis set will include all randomized subjects. Following the intention-to-treat (ITT) principle, subjects will be analyzed according to the group they were assigned to at randomization regardless of treatments received.

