In a modified ITT analysis set, we will exclude from the ITT sample those participants who –took less than 10% of whey protein isolate or KHCO₃ and those with any major protocol deviation.

In a per protocol analysis set, we will further restrict the mITT sample to participants who took whey protein isolate and KHCO₃ throughout the 24 weeks with an average compliance of at least 75%.

6. Trial Population

a. Eligibility

The inclusion criteria are:

- ambulatory community-dwelling men and women age ≥ 65 years
- habitual dietary intake of protein of ≤ 0.8 g/kg/d and not be vegetarian

- willing not to change their habitual diet, habitual exercise regimen, or enter into a weight loss program during the 24-wk study
- underactive based on the validated Rapid Assessment of Physical Activity (RAPA)
- estimated GFR $\geq 50 \text{ ml/min}/1.73 \text{ m}^2$

Participants who are taking a daily calcium supplement (as carbonate, acetate, citrate) can participate in the trial if they are willing to switch to a calcium triphosphate supplement provided to them by the study.

The exclusion criteria are

- users of the following medications or supplements:
 1. oral glucocorticoid use for > 10 days in the last 3 months
 2. anabolic and gonadal hormones in the last 6 months
 3. Tamoxifen/raloxifene in the last 6 months
 4. regular use of alkali-producing antacids (> 3 times per week)
 5. potassium containing supplements or products (i.e., KCl or salt substitutes)
 6. NSAIDS >3 times per week
 7. antacids containing calcium carbonate, aluminum hydroxide, magnesium hydroxide, or calcium acetate
 8. insulin
 9. sulfonylureas
 10. SGLT2 inhibitors
- individuals with the following conditions/diseases:
 1. a lower extremity fracture in the last year
 2. kidney stones in the past 5 years
 3. creatinine clearance $< 50 \text{ ml/min}$ (MDRD equation)
 4. hyperkalemia (serum potassium $>5.3 \text{ mEq/L}$; normal range 3.5-5.3 mEq/L)
 5. elevated serum bicarbonate ($>33 \text{ mmol/L}$; normal range 21-33 mmol/L)
 6. serum calcium outside the range of 8.3-10.2 mg/dl
 7. uncontrolled diabetes mellitus (fasting blood >150 or hemoglobin A1c $>8\%$)
 8. untreated thyroid or parathyroid disease
 9. significant immune disorder
 10. current unstable heart disease
 11. Crohn's disease
 12. active malignancy or cancer therapy in the last year
 13. alcohol use exceeding 2 drinks/day
 14. current peptic ulcers or esophageal stricture
 15. milk protein allergy

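### SAP 5.c defines the mITT and per-protocol sets by intake of the two active products by name, so as written the per-protocol set keeps one arm and has no comparator

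*SAP*

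**What the plan says.** SAP 5.c defines three analysis sets. The full set is every randomized participant, analyzed as assigned. The mITT set excludes those who "took less than 10% of whey protein isolate or KHCO₃ and those with any major protocol deviation". The per-protocol set narrows the mITT set to "participants who took whey protein isolate and KHCO₃ throughout the 24 weeks with an average compliance of at least 75" per cent.

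SAP 4.a lists four arms and gives each product its own name. Whey protein isolate and KHCO₃ are the actives. The fourth arm, for example, is "maltodextrin powder + microcrystalline cellulose".

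SAP 4.d states: "For all objectives, we use a superiority framework and a factorial analysis (at-the-margins analysis". The contrasts are whey protein against none and KHCO₃ against none. SAP 7.b then repeats the analyses in the mITT and per-protocol sets.

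Two places use looser language. SAP 5.b says "Adherence to the protein packets was assessed by packet counts and diaries", with no limit to the whey arms. Note j to the protocol's study procedures chart says "Subjects will take the whey protein supplement with each meal except on the days 164 and 168", although half the participants are assigned maltodextrin.

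**The concern.** A per-protocol set should contain participants who adhered to what they were assigned, in every arm. SAP 5.c instead asks whether they took the two actives. A participant in a placebo arm who took every packet and capsule took none of at least one active, and so fails the rule by complying with the allocation.

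SAP section 1 says the document is to give analysts clear specifications for deriving variables, agreed before outcome data are seen by group. Set membership is such a derivation. As it stands, an analyst must either follow the text and lose the comparators, or replace it with an unwritten rule.

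**Working it through.** **Inputs.** Four arms, 1:1:1:1 (SAP 4.a). Thirty per arm, 120 in all (SAP Table 1; the protocol's Objectives and Endpoints gives 120 as completers). Thresholds of 10% and 75% (SAP 5.c). For power: differences of 6 and 8 points, SDs of 12 and 15, two-sided 0.05 (SAP 4.c). Assumption: everyone takes all of the assigned product, which gives the largest possible sets.

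**1. The plan's own figure.** This point disputes no number in the plan; the power is a reference level. With power = Φ(δ/SE − 1.96) and SE = SD × √(2/60):
- KHCO₃: SE = 12 × 0.1826 = 2.191; 6/2.191 = 2.739; Φ(0.779) = 78.2%.
- Whey: SE = 15 × 0.1826 = 2.739; 8/2.739 = 2.921; Φ(0.961) = 83.2%.

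The SAP states 80% for both.

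**2. The rules applied to each arm.**

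| Arm | Whey isolate taken | KHCO₃ taken | mITT, *or* = either | mITT, *or* = both | Per protocol |
|---|---|---|---|---|---|
| Whey + KHCO₃ | 100% | 100% | kept | kept | kept |
| Whey + cellulose | 100% | 0% | out | kept | out |
| Maltodextrin + KHCO₃ | 0% | 100% | out | kept | out |
| Maltodextrin + cellulose | 0% | 0% | out | out | out |
| Total | | | 30 | 90 | 30 |

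A participant from another arm who was given both actives by mistake does not re-enter. SAP 5.b makes failure to "receive the randomly allocated intervention" a major deviation, which removes that person from the mITT set and therefore from the per-protocol set.

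**3. Estimability.** The model needs an intercept, a whey indicator and a KHCO₃ indicator. In the whey + KHCO₃ arm alone all three columns equal 1, so the design has rank 1 of 3 and neither effect can be estimated. This does not depend on the arm size. The set is 30/120 = 25% of the planned number.

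**4. mITT if *or* means both.** Three arms of 30 remain and the rank is 3 of 3. Without the double-placebo arm, the whey effect rests on whey + KHCO₃ against maltodextrin + KHCO₃, and the KHCO₃ effect on whey + KHCO₃ against whey + cellulose, each 30 against 30. SE = SD × √(1/30 + 1/30) = SD × 0.2582.
- KHCO₃: 12 × 0.2582 = 3.098; Φ(6/3.098 − 1.96) = Φ(−0.023) = 49.1%.
- Whey: 15 × 0.2582 = 3.873; Φ(8/3.873 − 1.96) = Φ(0.106) = 54.2%.

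Both contrasts can be estimated, but the per-protocol step still reduces the set to one arm.

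**5. Assigned-product reading.** All four arms stay, up to 120, with 60 against 60 on each margin. The documents give no adherent share for this trial. If it is assumed equal across arms at 60% to 100%, each side of a margin has 36 to 60 participants, and power is 56% to 78% for KHCO₃ and 62% to 83% for whey.

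**The case against.** The strongest reply is that nobody would run the literal rule. It would exclude correctly treated placebo recipients and defeat the factorial analysis that SAP 4.d requires. SAP 5.b counts adherence on study pills and protein packets, and note j uses the active name for everyone, so the active names look like shorthand. A statistician would notice a one-arm set at once. This stands as evidence of intent, and I accept that the assigned products were probably meant. It does not repair the text: the names in 5.c are those SAP 4.a gives to the actives, and nothing in either document ties the 10% and 75% thresholds to the assigned product.

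The reply is also right that the mITT collapse depends on how *or* is read (step 4).

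A reader might infer more: that membership is undefined even on the assigned-product reading, because no compliance denominator is given. The protocol says "On days 1-14, participants will take 1 capsule after each meal", and two after each meal from then on, so the schedule is 14 × 3 + 154 × 6 = 966 capsules. Someone who stayed on the starting number would take 168 × 3 = 504, or 52.2%; with every packet taken, the mean of the two products is (52.2 + 100)/2 = 76.1%. That participant is constructed to fall on either side of the cut-off. The documents do not say that such cases are common; in the sponsor's earlier 12-week capsule trial, mean adherence at 81 mmol/d was 91.3%. The stated schedule is the natural denominator, and the requirement of intake over the whole 24 weeks largely settles participants whose product was stopped. Only the choice between each product and their mean remains truly open.

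**Conclusion.** The wording is wrong as written. The per-protocol set contains only the whey + KHCO₃ arm, at most 30 of 120, on either reading of *or*. The mITT set contains the same 30 if *or* means either product, and 90 if it means both. The counts assume the planned arm sizes and full adherence; the absence of a per-protocol comparator depends on neither.

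A reader might infer that the trial's main result is at risk. It is not: SAP 7.b places the primary analysis on the ITT sample, SAP 5.a treats secondary analyses as supporting, and no decision rule rests on these repeats. A reader might also infer a bias from applying the thresholds only to recipients of an active product. That would select the compared arms differently, but the documents do not say it will be done and do not allow its size to be estimated.

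The defect should be fixed, but it is confined to two supporting analysis sets.

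**What to change.** Reword SAP 5.c so that both sets rest on the assigned powder packets and assigned capsules, active or placebo, with identical thresholds in all four arms:

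- **mITT:** exclude participants who took less than 10% of their assigned packets or less than 10% of their assigned capsules, and those with a major protocol deviation. The sponsor should confirm that *or* means either product.
- **Per protocol:** from the mITT set, keep participants whose average compliance with assigned packets and capsules over the full 24 weeks is at least 75%. State whether 75% applies to each product or to their mean.

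The cost is a dated change to a few lines of the SAP, made before outcome data are examined by group. No new data are needed, because packet and capsule counts and diaries are already planned for all participants.
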